5.4 Treatment Assignment Procedures

5.4.1 Randomized Procedure

This is a double-blind, randomized, and controlled trial with a 1:1:1 ratio among three groups in Phase 2: 15 mcg/mL vaccine, 30 mcg/mL vaccine, and placebo; and 2:1 ratio between two groups in Phase 3: either 15 mcg/mL or 30 mcg/mL vaccine and placebo. Each subject will be assigned a unique screening number by the investigator after signing the informed consent.

The Investigator will maintain the screening/enrollment log. The log will contain essential information including subject name, date of screening, gender, date of birth, whether or not the subject meets eligibility criteria, whether subject is enrolled and date, and if not enrolled, reason why the subject is not enrolled or not randomized.

Once a subject identification number has been assigned to a subject, it will not be used again. Additional subjects may be randomized into the study at the discretion of the sponsor in the case of any subject who is randomized but does not receive any study vaccine.

The permuted randomization block design procedure will be used to generate the randomization schedules for both Phase 2 and Phase 3. The randomization will be stratified by province and age group (18-40 years of age and 41-60 years age). The block size for each part will be chosen based on the number of treatment groups and anticipated enrollment sizes at each province.

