8.2 Laboratory Evaluations

8.2.1 Clinical Laboratory Evaluations

All biochemical, immunological, and hematological testing will be performed at labs that have been certified within Vietnam. Some samples may be sent to an additional lab for feedback and assistance to the Vietnam laboratory on testing methods. These outside test results are for technical assistance only and will not be considered in the analysis.

Laboratories will follow written procedures for conducting all laboratory assays.

Laboratory reference ranges will be specified for all tests prior to enrollment of any subject. The reference ranges will be developed based on a survey of ranges from national and regional hospital laboratories. A Toxicity Grading Table will be used to facilitate the grading of the selected out-of-range laboratory parameters (see Appendix B).

A laboratory result that is out-of-range but below Grade 2 does not qualify as an AE to be recorded, and does not require determination of clinical significance or relatedness. A result will be checked as not clinically significant “NCS” if it is outside the lab range but does not rise to a Grade 2 on the AE Table.

Serology for Chronic Viral Hepatitis Infections (PHASE 2 ONLY)

Blood specimens will be evaluated for the following using tests qualified in Vietnam:

- Hepatitis B virus surface antigen (HBsAg)
- HCV antibody using anti-HCV test

Specimen collection will occur on Day S1. Determinant results of a subject’s testing must be obtained from the laboratory prior to administration of any study product.

Pregnancy Test

In order to confirm pregnancy status of females who are able to become pregnant, a qualitative human chorionic gonadotropin (hCG) test will be done on a urine sample.

Pregnancy testing will be done on fertile women on Days S1, S2/D1, and D22. No injection of study product may be given to a fertile woman without a pregnancy test being done or to any woman with a positive pregnancy test.

Clinical Safety Laboratory Tests for Screening and Follow up (PHASE 2 SUBJECTS ONLY)

To monitor potential vaccine toxicity for PHASE 2 SUBJECTS ONLY, blood specimens (fasting not required) will be collected at screening on Day S1, Day 8, Day 22, and Day 29 and evaluated for the following using tests qualified in Vietnam.

- Creatinine
- Alanine aminotransferase (ALT)
- Total bilirubin
- Total protein
- Number of WBC
- Hemoglobin content (Hgb)
- Platelet count

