9.2 Methods and Timing for Assessing and Recording Safety Parameters

9.2.1 Adverse Events

An AE is defined as any untoward medical occurrence in a patient or clinical investigation participant administered a pharmaceutical product, which does not necessarily have a causal relationship with this treatment. An AE can therefore be any unfavorable and unintended sign (including an abnormal laboratory finding), symptom, or disease temporally associated with the use of a medicinal product,

whether or not considered related to the medicinal product. Information to be collected on AEs includes event description, time of onset, clinician's assessment of severity, relationship to study product, and time of resolution/stabilization of the event. AE assessment should be made only by those with the training and authority to make a diagnosis.

In this protocol, laboratory results are considered AEs when the result is Grade 2 or above.

Any medical condition that was present at the time that the subject was enrolled should not be reported as an AE, but should be reported as a pre-existing condition on the Medical History Form. However, if this condition occurs with greater frequency or severity during the study, it should be recorded as an AE.

AEs, including laboratory abnormalities that are Grade 2 and above, should always be assessed for severity and relationship to study products.

This study will collect and record solicited local and systemic reactogenicity and unsolicited AEs. For clarity, solicited reactogenicity refers to AEs specifically asked about during the 7-day post-vaccination period. Unsolicited events are those not specifically solicited, but may be reported by the subject at any time or observed by study staff while the subject is at a clinic for a study visit. If a new solicited event is reported by the subject outside of the 7-day post-vaccination window, this event will be recorded as an "unsolicited AE" because it will be outside of the 7-day window for collection of solicited reactogenicity.

SAEs are defined in Section 9.2.8.

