9.2.4 Guidelines for AEs

To improve the quality and precision of acquired AE data, the PI should observe the following guidelines:

- Whenever possible, use recognized medical terms when recording AEs on the AE CRF. Do not use colloquialisms and/or abbreviations.
- If known, record the diagnosis (i.e., disease or syndrome) rather than component signs, symptoms, and laboratory values on the AE CRF (e.g., record congestive heart failure rather than

dyspnea, rales, and cyanosis). However, signs and symptoms that are considered unrelated to an encountered syndrome or disease should be recorded as individual AEs on the CRF (e.g., if congestive heart failure and severe headache are observed at the same time, each event should be recorded as an individual AE).

- AEs occurring secondary to other events (e.g., sequelae) should be identified by the primary cause. A “primary” AE, if clearly identifiable, generally represents the most accurate clinical term to record on the AE CRF. If a primary serious AE (SAE) is recorded on an SAE CRF, events occurring secondary to the primary event should be described in the narrative description of the case.

For example:

Orthostatic hypotension → Fainting and fall to floor → Head trauma → Neck pain

The primary AE is orthostatic hypotension.

- Out of range laboratory results that are Grade 2 or higher will be considered AEs and should be entered onto an AE form.
- Death is an outcome of an event. The event that resulted in the death should be recorded and reported on the SAE CRF.
- For hospitalizations related to surgical or diagnostic procedures, the illness leading to the surgical or diagnostic procedure should be recorded as the SAE rather than the procedure itself. The procedure should be recorded in the case narrative as part of the action taken in response to the illness.
- Pregnancies are not considered AEs. They will be recorded on a separate Pregnancy CRF. Pregnancy outcomes that include stillbirth and any congenital anomalies must be reported as SAEs.

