12.2 Sample Size Considerations

This is an operational, seamless Phase 2/3 trial with a primary objective to evaluate the immunogenicity and safety of two dose levels of IVACFLU-A/H5N1, 15 mcg vs. 30 mcg (study Phase 2), and select the optimal of the two doses to evaluate further for potential licensure (study Phase 3). The sample size for this study was selected for the primary immunogenicity analysis and the safety analysis to satisfy the licensure requirements by the MOH. The sample size for Phase 2 of the study is approximately 300 subjects (100 per group), and for Phase 3, 1500 subjects (1000 for the IVACFLU-A/H5N1 group and 500 for the placebo group).

Overall, a total of approximately 1100 subjects will receive the selected dose of study vaccine, which will allow for the recognition of SAEs occurring at a frequency of less than one percent. The probability of observing at least one vaccine-related serious adverse event among 1100 subjects is greater than 90 percent if the true rate of such events is 0.21 percent. If no vaccine-related serious adverse events are observed in 1100 vaccinees receiving IVACFLU-A/H5N1, this would represent an upper bound of the two-sided 95 percent Confidence Interval (CI) on the percentage of such events of 0.3 percent.

Sample Size	No. of Events	Exact Two-Sided 95% CI
N=1100	0 events	[0.0%, 0.33%]
	1 event	[<0.01%, 0.51%]
	2 events	[0.02%, 0.65%]
	5 events	[0.15%, 1.06%]
	10 events	[0.44%, 1.67%]

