This IVACFLU-A/H5N1 Phase 2/3 is a double-blind, randomized, placebo-controlled trial to test the safety and immunogenicity of two doses given 21 days apart of the IVAC A/H5N1 vaccine. Subjects will be male and female healthy adults from 18 through 60 years of age. In the Phase 2 study which was a dose-selection study and was conducted at one site (Khanh Hoa), 300 male and female healthy adult subjects from 18 through 60 years of age were randomized to receive 15 mcg of vaccine (n=100), 30 mcg of vaccine (n=100), or saline placebo (n=100). The details of the interim analysis plan for the Phase 2 study had been prepared separately.

The Phase 3 is a confirmatory study that will expand the safety and immunogenicity in a larger number of subjects to meet product registration in Vietnam. In Phase 3, subjects will be randomized to receive the selected vaccine 15 mcg dose (n=500) or saline placebo (n=100) under double blind. Safety will be assessed in all subjects and immunogenicity will be measured by Hemagglutination Inhibition test (HAI) in a subset of approximately 270 subjects receiving the IVACFLU-A/H5N1 (n=225 vaccinees) and placebo (N=45) from all subjects enrolled at one of 2 study sites (Hai Phong) in Phase 3.

This final analysis plan will mainly focus on the analyses of Phase 3 cohort with additional analyses combining subjects from both phases if needed.

I. OBJECTIVES

The study objectives and endpoints for Phase 3 as described in the protocol are as follows:

Primary Objective	Endpoint

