If a solicited sign or symptom has started during the 7 days post vaccination and continues beyond the 7 days, it will continue to be reported as a reactogenicity symptom. Any solicited sign or symptom starting after 7 days post vaccination will be recorded as an “unsolicited AE”. Adverse reactions will be graded (i.e., Grade 1 to 4).

- **Unsolicited adverse events** are any AEs that occur any time after the vaccine/placebo is given (temporally related to study product), whether or not deemed “related” to the product, and are not solicited (specifically asked of the subject). Unsolicited AEs can be observed by study staff while the subject is at a clinic for a study visit or reported by the subject at any time, and subcategorized as those deemed related to vaccination or not by a study clinician.

- **Serious adverse events (SAEs)** occur from vaccination through 3 months (Days 1-91) post-vaccination, identified or observed by study staff and/or reported by parent at any time. SAEs will be graded for severity and subcategorized as those deemed related to vaccination or not by a study clinician. All SAEs will be listed.
- **Targeted physical examination and vitals data** will be summarized for post-vaccination measurements, separately by visit or time point of observation.

Analysis Methods

In general, adverse events (AEs) will be summarized by MedDRA System/Organ Class (SOC) and adverse event type (MedDRA Preferred Term), using the MedDRA dictionary in production at FHI 360 at the time the database is developed. As needed, this AE summary will be repeated for (a) AEs considered related to study product and (b) serious AEs (SAEs).

Unsolicited AE summaries will report the number of persons with at least one episode of the given AE type/SOC, as well as the number of episodes. In calculating percentages, each person will contribute only once to a given AE type/SOC no matter the number of episodes experienced. Percentages of subjects experiencing each reaction or event, or at least one reaction or event, will be calculated along with two-sided exact (Clopper-Pearson) binomial 95% CIs.

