For the solicited local and systemic/general adverse events, Fisher's exact test for two proportions or the Cochran-Mantel-Haenszel test⁵ for severity grade categories at 2-sided 0.05 alpha will be used to compare the treatment groups. No formal hypothesis testing with multiplicity adjustment will be performed. Furthermore, no statistical testing will be performed for unsolicited AEs including SAEs.

In addition, subject listings of adverse events will include details such as the following: MedDRA codes, study day of onset, seriousness, duration, action/treatment, outcome, severity, relatedness, and current status. Concomitant medications will also be coded and listed.

Furthermore, additional analyses will be repeated by combining safety outcomes of the selected dose group and placebo group from both Phases 2 and 3 cohorts if needed.

⁵ The Cochran-Mantel-Haenszel test is better method for comparing severity grade categories than the Chi-squared test as proposed in the study protocol

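### The final SAP's optional pooled Phase 2 and 3 safety analysis ignores phase, although vaccine:placebo is 1:1 in Phase 2 and 5:1 in Phase 3

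*SAP*

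**What the plan says.** The final SAP, Section VIII (Analysis Methods), closes with an optional supplement: "analyses will be repeated by combining safety outcomes of the selected dose group and placebo group from both Phases 2 and 3 cohorts if needed". The methods it would repeat come just before it.

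- **All events.** "Percentages of subjects experiencing each reaction or event, or at least one reaction or event, will be calculated", with exact confidence intervals, by group. The denominator is the Full Analysis Population, meaning everyone vaccinated.
- **Solicited events only.** Fisher's exact test for proportions, or CMH for severity grades, two-sided at 0.05. Footnote 5 presents CMH as a replacement for the protocol's chi-squared test on grades. No strata are listed.
- **Unsolicited events, including SAEs.** Described, not tested.

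The allocation differs by phase. Protocol 5.4.1 randomises "with a 1:1:1 ratio among three groups in Phase 2", which is 100 per arm. The final SAP Preface says that in Phase 3 "subjects will be randomized to receive the selected vaccine 15 mcg dose (n=500) or saline placebo (n=100) under double blind". Protocol 12.2 instead gives "1500 subjects (1000 for the IVACFLU-A/H5N1 group and 500 for the placebo group".

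So does the laboratory schedule. Protocol 8.2.1 states: "To monitor potential vaccine toxicity for PHASE 2 SUBJECTS ONLY, blood specimens (fasting not required) will be collected". Protocol 9.2.1 states: "In this protocol, laboratory results are considered AEs when the result is Grade 2 or above". Section 9.2.4 adds: "Out of range laboratory results that are Grade 2 or higher will be considered AEs and should be entered onto an AE form".

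**The concern.** Within each phase, vaccine and placebo are comparable by randomisation. Adding the phases together loses that protection if the allocation ratio and the background event rate both change between them. The pooled placebo group would be half Phase 2 subjects and the pooled vaccine group mostly Phase 3 subjects, so a difference between phases would appear as a difference between treatments.

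One such difference is built into the design. A laboratory event can be found routinely only in Phase 2, yet Phase 3 subjects would sit in the pooled denominators as though they had been tested. They make up far more of the vaccine denominator than of the placebo denominator, so the vaccine percentage is diluted more. Phase 3 is the confirmatory study for registration, and a pooled table of this kind could show a liver-test signal reduced or reversed by the bleeding schedule alone.

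**Working it through.** **Plan's own figure.** The documents give no pooled vaccine-placebo comparison. The one stated figure that rests on combined phases is the SAE statement in Protocol 12.2, for 100 + 1000 = 1100 recipients. It reproduces: 1 − (1 − 0.0021)^1100 = 0.901, and the upper exact limit for 0/1100 is 0.33%. It concerns one arm, so this problem does not touch it, but it shows that combining the phases is part of the safety reasoning.

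**Phase 2 share of each pooled arm**

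| Phase 3 sizes | Vaccine | Placebo | Vaccine minus placebo |
|---|---|---|---|
| SAP, 500:100 | 100/600 = 16.7% | 100/200 = 50.0% | −0.333 |
| Protocol, 1000:500 | 100/1100 = 9.1% | 100/600 = 16.7% | −0.076 |

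**General bias.** Let the background rates be r2 (Phase 2) and r3 (Phase 3), and let the risk difference d be the same in both phases. With SAP sizes:

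crude pooled difference = d + (100/600 − 100/200)(r2 − r3) = d − (r2 − r3)/3

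The bias is zero when r2 = r3. It hides a vaccine risk when Phase 2 is higher and inflates it when Phase 3 is higher.

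**Laboratory events (no rate assumed).** Take no laboratory events in Phase 3, since no tests are scheduled there, and Full Analysis denominators. With Phase 2 rates v and p:

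pooled ratio = (100v/600) ÷ (100p/200) = (v/p) × 0.333

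- With 1000:500 the multiplier is (100/1100)/(100/600) = 0.545.
- Break-even Phase 2 ratios are 1/0.333 = 3.0 and 1/0.545 = 1.83. Below these, the vaccine reads lower than placebo.
- Illustration with assumed Phase 2 rates of 6% and 3% (ratio 2.0): 6/600 = 1.0% against 3/200 = 1.5%, a ratio of 0.67.
- Equal Phase 2 counts of 10 and 10 give a crude ratio of 0.33. The Mantel-Haenszel ratio stratified by phase is 1.00.

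Such events do occur. Protocol Table 6 (Phase 1) lists 5 ALT or bilirubin events in 63 vaccinees, 1 of them among the 32 given 15 mcg, and none in 12 placebo subjects.

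**Solicited events (background rates assumed, no vaccine effect).** Rejection rate of crude pooled Fisher at two-sided 0.05, computed exactly from the binomial distributions:

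| Phase 2 / Phase 3 rate | SAP sizes: bias (points) | SAP sizes: rejection | 1000:500: bias (points) | 1000:500: rejection |
|---|---|---|---|---|
| 20% / 20% | 0 | 4.5% | 0 | 4.6% |
| 25% / 20% | −1.7 | 7.3% | −0.4 | 5.1% |
| 30% / 20% | −3.3 | 15.2% | −0.8 | 6.2% |
| 20% / 25% | +1.7 | 6.8% | +0.4 | 4.9% |
| 20% / 30% | +3.3 | 13.7% | +0.8 | 5.8% |

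CMH stratified by phase, in 200,000 simulations with SAP sizes, rejected in 4.9% to 5.1% at 20/20, 25/20, 30/20 and 20/30.

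**With a true excess of 5 points in both phases (SAP sizes)**

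- 30/20: vaccine (100 × 0.35 + 500 × 0.25)/600 = 26.7%, placebo 25.0%, crude difference +1.7.
- 20/30: vaccine (100 × 0.25 + 500 × 0.35)/600 = 33.3%, placebo 25.0%, crude difference +8.3.
- The Mantel-Haenszel risk difference is +5.0 in both.

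**The case against.** The strongest reply is about weight. The pooled analysis is a supplement that may never be run, and the final SAP says its focus is Phase 3. By-phase results will exist: the interim SAP already compares Phase 2 safety by arm through Day 43, after the last laboratory draw. No pooled ratio or separate laboratory category is planned; these events would appear only as preferred terms among untested unsolicited events. For any unsolicited event the dilution is mild: with an assumed 5% laboratory and 20% other events, the no-effect ratio is 0.93. Exact intervals beside the percentages would also temper the reading: 6/600 gives 0.37% to 2.16% and 3/200 gives 0.31% to 4.32%. The solicited-event results rest on assumed phase gaps, in tests described as non-formal, and the largest need a 10-point gap. A 3.3-point bias would not alter a contrast as large as the Phase 1 local reactions (75% at 15 mcg, 25% placebo). With 1000:500 the distortion is small. Finally, the SAP is silent on stratification; it does not exclude it.

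Most of this is true and limits the severity. It does not remove the problem. Followed as written, the SAP produces unstratified percentages and an unstratified Fisher test, and naming CMH for severity grades does not make phase a stratum. Percentages by group will be read side by side whether or not a ratio is printed. Sound Phase 2 tables elsewhere do not correct a pooled table that contradicts them, and leaving the method open allows it to be chosen after unblinding.

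**Conclusion.** The concern holds, as a point that should be corrected but does not threaten the main analysis. With the SAP's sizes, the crude pooled comparison carries a bias of one third of any phase difference in background rate, given a common risk difference across phases. With the protocol's sizes it is about 0.076 of that difference.

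For laboratory events the pooled ratio is one third of the Phase 2 ratio (0.55 with 1000:500), whatever the rate. This assumes all-subject denominators and no laboratory events recorded in Phase 3, and it takes the laboratory schedule from the supplied protocol, whose Phase 3 sizes differ from the SAP's. It applies to laboratory terms, not to unsolicited events overall. For solicited events the size and direction are unknown, because no rates by phase are given.

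**What to change.** In Section VIII of the final SAP:

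1. State that any vaccine-placebo safety comparison combining the phases is stratified by phase, using CMH with phase as the stratum and a Mantel-Haenszel risk difference, and that percentages are also shown for each phase.
2. Report adverse events arising from protocol laboratory tests on Phase 2 denominators only.
3. Reconcile the Phase 3 sizes (500:100 in the SAP, 1000:500 in the supplied protocol) and state which apply.

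The cost is two or three sentences and one stratum variable in existing programs. Phase is already recorded for every subject, and no new data are needed.
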